1. LIST OF ABBREVIATIONS AND DEFINITIONS OF TERMS

AE(s)	adverse event(s)
CCI	
ANCOVA	analysis of covariance
ATC	anatomical therapeutic chemical
BMI	body mass index
CI(s)	confidence interval(s)
cm	centimeters
CMH	Cochran-Mantel-Haenszel
ECG	electrocardiogram
FDA	Food and Drug Administration
FDC	Fixed dose combination
HR	heart rate
hr(s)	hour(s)
ITT	intent-to-treat
kg	kilograms
LOCF	last observation carried forward
LSMean	least square mean
max	maximum
MedDRA	Medical Dictionary for Regulatory Activities
mg	milligram
min	minimum
n	number of observations
N	number of subjects (sample size)
OTC	over-the-counter
PP	per-protocol
PT	preferred term
SAE(s)	serious adverse event(s)
SAS®	Statistical Analysis System (SAS® Institute Inc., Cary, NC)
SD	standard deviation
SOC	system organ class
SPID	Sum of pain intensity difference
TEAE(s)	treatment-emergent adverse event(s)

Statistical Analysis Plan

Bayer 21069

Version: v1

Date: 13 May 2020

TOTPAR	Total pain relief
US	United States
WHO-DDE	World Health Organization Drug Dictionary

2. INTRODUCTION**2.1 Background**

In the United States, naproxen has been marketed as a prescription medication since 1976 under the brand name Naprosyn®. Its sodium salt, naproxen sodium, was first sold under the trade name Anaprox® in 1980. In 1994, the US Food and Drug Administration (FDA) approved naproxen sodium tablets (using the brand name Aleve®), 220 mg for over-the-counter (OTC) use. Aleve is indicated for the temporary relief of minor aches and pains due to: minor pain of arthritis, muscular aches, backaches, menstrual cramps, headaches, toothaches, and the common cold. It also temporarily reduces fever. As an OTC medication, Aleve should not be taken for longer than 10 days for pain or 3 days for fever unless otherwise directed by a physician.

This dose ranging study is intended to find the minimum effective dose of caffeine to potentiate the analgesic effect of naproxen sodium.

Participants who need to have third molar extraction will be solicited to participate in this study. Participants who consent to participate may benefit by receiving a medical exam, dental radiographs and no-cost surgical procedures for teeth extraction. Furthermore, post-surgical participants will be provided continuous nursing care for approximately 12 hours after surgery. Potential risks of the surgical procedure include pain, dry socket, infection, swelling, bleeding, trismus, and lip or tongue numbness. Potential risks related to local anesthesia and mild sedation include paresthesia and drowsiness. Participants who experience a treatment failure can have the option of taking a standard rescue medication commonly used for post-operative pain relief. Potential study medication benefit will be relief of postsurgical pain, which is highly prevalent following extraction of wisdom teeth. Potential risks of a single dose of OTC study medication are low and described in the Drug Facts Label.

During the study, participants will be closely monitored for evidence of adverse events. Weighing between the potential risks associated with the study and given the ability to mitigate risks through close monitoring and routine peri-operative care, this study is considered clinically and ethically acceptable.

CCI

Statistical Analysis Plan

Bayer 21069

Version: v1

Date: 13 May 2020

2.2 Study Rationale

CCI

This study is intended to find the optimal dose for caffeine to be added to CCI naproxen sodium in a single tablet. This study will also compare the analgesic efficacy of CCI

CCI

3. STUDY OBJECTIVES

The primary objective of this study will be to compare a single oral dose of the FDC relative to naproxen sodium CCI Caffeine CCI and placebo.

The secondary objectives of this study will be to:

- To compare a single oral dose of the FDC relative to naproxen sodium CCI Caffeine CCI and placebo. The assessments are made in terms of:
 - Pain intensity differences Measures of pain relief
 - Duration of analgesic efficacy
 - CCI
 - CCI
 - Overall relief from pain based on measures of pain intensity and pain relief
 - Global assessment of the investigational product
- CCI
- To assess the safety and tolerability of the investigational product in terms of adverse events (AEs) and clinical parameters

4. STUDY DESIGN

4.1 Overall Study Design

This is a single center, randomized, double-blind, parallel, placebo-controlled study in participants experiencing moderate to severe postoperative dental pain. The study will consist of a Prescreening telephone call, a Screening Visit, a one-day Treatment Period and a Post-Operative phone call or visit. Eligible participants who have undergone surgical extraction of three or four third molars, 2 of which were mandibular partial or full bony impacted third molars will be kept in-house and evaluated for efficacy and safety at the study site through completion of all trial procedures.

Qualified participants will then be randomized into one of seven treatments. Approximately 300 participants will be screened prior to surgery. Approximately 190 will have surgery and approximately 180 will be randomized to a specific treatment.

The duration of each participant’s participation will be approximately 37 days. For an overview on the study design and study procedures see Figure 1.

	Screening Phase	Treatment Phase				Follow up Phase
Trial Days	Day -28 to -1	Day 1 Pre-surgery	Day 1 Surgery	Day 1 Post-surgery	Day 1	2-5 days after discharge
		Check-in to study site	Surgical teeth extraction	Categorical pain NRS pain	* Stopwatch method NRS pain relief Global assessment	Phone call or visit

= randomized study intervention of: naproxen sodium/caffeine [Redacted]
 naproxen sodium/caffeine [Redacted]
 naproxen sodium/caffeine [Redacted]
 naproxen sodium/caffeine [Redacted]
 naproxen sodium [Redacted]
 caffeine [Redacted]
 or placebo.

4.1.1 Schedule of Visits and Assessments

The schedule of assessments can be found in Section 1.3 of the protocol.

4.1.2 Method of Assigning Subjects to Treatment Groups

On Day 1, participants will be assigned a unique number (randomization number) in ascending numerical order at the study site. The randomization number encodes the participant's assignment to one of the seven (7) arms of the study, according to the randomization schedule generated prior to the study by the Sponsor. Each participant will be dispensed blinded study intervention, labeled with his/her unique randomization number, throughout the study.

4.1.3 Blinding

Participants enrolled in the trial, investigators and their staff involved in protocol procedures or who are involved in data collection, data entry and data analysis will be blinded to the identity of the treatments until the database is locked. The study monitor will conduct product accountability after database lock. To preserve blinding, participants will be blindfolded during administration of study medication. Study drug will be dispensed by an unblinded study team member based on the randomization schedule. That team member may have no other role in the study conduct and may not reveal the study drug's identity to any members of the blinded study team.

Sponsor will supply study medication in bulk containers. Selection of the proper dose for an individual participant will be performed by an unblinded study team member using the provided randomization schedule. The unblinded study team member will withdraw the appropriate study medication from the bulk container and transfer it to a dispensing cup. All study interventions must be administered as 2 tablets per participant. Some study interventions require the addition of a placebo tablet. The unblinded study team member will then bring the study medication to the treatment room where it will be dispensed to the participant by the study team member. The unblinded study team member should have no other responsibilities in the study.

5. EFFICACY AND SAFETY ENDPOINTS

5.1 Efficacy Endpoints

5.1.1 Primary Efficacy Endpoints

The primary efficacy endpoint is the Sum of Pain Intensity Difference over 8 hours (SPID0-8).

5.1.2 Secondary Efficacy Endpoints

The secondary efficacy endpoints are as follows:

- Total Pain Relief over 8 hours (TOTPAR0-8)
- Time to first use of rescue medication.
- SPID0-2, SPID0-4, SPID0-12
- TOTPAR0-2, TOTPAR 0-4, TOTPAR0-12, TOTPAR8-12
- Pain Intensity Difference (PID) at 0.5, 1, 1.5, 2, 3, 4, 5, 6, 7, 8, 9, 10, 11, and 12 hours post-dose
- Pain Relief Scores at 0.5, 1, 1.5, 2, 3, 4, 5, 6, 7, 8, 9, 10, 11, and 12 hours post-dose
- CCI [REDACTED]
- [REDACTED]
- CCI [REDACTED]
- CCI [REDACTED]
- Cumulative proportion taking rescue medication by timepoint
- Peak PID
- Peak Pain Relief
- CCI [REDACTED]
- Global Assessment of the investigational product

5.2 Safety Endpoints

Safety will be assessed by reports of adverse events (AEs), urine laboratory results, and absolute and change from baseline in vital signs.

6. STATISTICAL AND ANALYTICAL PLANS

6.1 General Methodology

CCI [REDACTED]

CCI [REDACTED]

CCI

Reported AEs, medical history terms, and prior and concomitant procedures and therapies will be classified on the basis of Medical Dictionary for Regulatory Activities (MedDRA) terminology version 22.1 or later. Prior and concomitant medications as well as rescue medication will be classified on the basis of World Health Organization Drug Dictionary Enhanced (WHO-DDE) terminology version March 2019 or later.

6.1.1 Statistical Analysis

CCI

6.1.2 Baseline Definition

Baseline is from the last measurement prior to study treatment.

6.1.3 Visit Windowing

Visits will not be windowed. Visits will be summarized and listed by their nominal value.

6.1.4 Adjustments for Covariates

Baseline pain intensity will be used as a covariate for the efficacy analysis where appropriate.

6.1.5 Handling of Dropouts or Missing Data

CCI

If a partial date is reported where the day is missing, then the day will be imputed as the first day of the month unless the month is the same month as the first dose then the day will be that of first dose with the month and year remaining the same. If a partial date is reported where the month is

missing, then the month will be imputed to January unless the year is the same year as the first dose then the month will be that of first dose with the year remaining the same. If a partial date where both the day and month is missing, follow details as stated previously.

Missing AE start dates will be imputed using partial date imputation rules as previously described in this Section. Missing data for other parameters will not be imputed for analysis unless otherwise defined.

6.1.6 Interim Analyses and Data Monitoring

No interim analysis or data monitoring is planned for this study.

6.1.7 Multicenter Studies

Not applicable to this study.

6.1.8 Multiple Comparisons/Multiplicity

No adjustments for multiple comparisons or multiplicity will be made.

6.1.9 Use of an Efficacy Subset of Subjects

The PP population will be used for the primary analysis.

6.1.10 Active-Control Studies Intended to Show Equivalence

Not applicable to this study.

6.1.11 Examination of Subgroups

Not applicable to this study.

6.2 Disposition of Subjects

The number of subjects enrolled, randomized, completed, and discontinued (including the reasons for discontinuation) will be summarized for each treatment group.

6.3 Protocol Deviations

Protocol deviations will not be entered into the database. Deviations leading to exclusion from analysis populations will be identified and summarized. All deviations will be provided to CCI via an Excel file prior to database lock and will be presented in a by-subject listing.

6.4

CCI [REDACTED]

CCI [REDACTED]

CCI [REDACTED]

CCI [REDACTED]

[REDACTED]

CCI [REDACTED]

CCI [REDACTED]

CCI [REDACTED]

[REDACTED]

- | [REDACTED]
- | [REDACTED]
- | [REDACTED]
- | [REDACTED]

[REDACTED]

6.5 Demographic and Other Baseline Characteristics

All baseline summaries will be done on the ITT, PP, and Safety populations.

Sex, race, and ethnicity will be summarized by counts and percentages. Age, height (cm), weight (kg), and body mass index (BMI) will be summarized with descriptive statistics by treatment group and overall.

Oral surgery site will be presented by frequency counts and percentages for each treatment group and overall. Number of teeth extracted, impaction scores, and duration of surgery (first incision to last suture) will be summarized with descriptive statistics by treatment group and overall. All dental surgery information and oral examination data will be presented in by-subject listings.

Baseline pain score will be summarized with frequency counts and percentages as well as with descriptive statistics by treatment group and overall.

Social history (drug, alcohol, tobacco, and caffeine use) will be summarized with frequency counts and percentages by treatment group and overall. Social history will also be presented in a by-subject listing.

Medical histories / surgeries will be coded using the MedDRA dictionary and presented in a by-subject listing. Inclusion / exclusion criteria will also be presented in by-subject listings.

6.6 Prior and Concomitant Medications

Concomitant medications will be coded to preferred name and Anatomical Therapeutic Chemical (ATC) classification of ingredients using the WHO-DDE.

Medications which start prior to first dose will be considered prior medications. Ongoing medications and medications ending after the date of first dose will be considered concomitant medications. Incomplete start and end dates which could be either prior to first dose or after first dose will be considered prior to first dose.

A by-subject listing of all prior and concomitant medications will be presented. Concomitant medications will summarize drug class and preferred name by treatment group and overall for each population.

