6.9.2 Adverse Events

All AEs that occur during the study will be recorded and classified on the basis of Medical Dictionary for Regulatory Activities (MedDRA) terminology. Treatment-emergent AEs (TEAEs) are defined as AEs with an onset on or after the date of the first study drug administration. AEs noted prior to the first study drug administration that worsen after baseline will also be reported as AEs and included in the summaries.

TEAEs will be summarized by treatment group, the number of subjects reporting a TEAE, system organ class, preferred name, severity, relationship to study treatment (causality), and seriousness. When summarizing TEAEs by severity and relationship, each subject will be counted once within a system organ class or a preferred term by using the event with the highest severity and greatest relationship within each classification.

Serious AEs (SAEs) will be summarized.

The number and percent of subjects who experience any event, by System Organ Class (SOC), and by Preferred Term (PT) will be displayed by treatment group for the Safety population.

All adverse events and all serious adverse events will be presented in individual listings. In addition, a list of subjects who prematurely discontinue from the study due to an AE will be provided.

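### SAP 6.6 can file a drug taken after dosing as prior only, and so omit it from the concomitant-medication table, when both its dates are incomplete

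*SAP*

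**What the plan says.** SAP 6.6 (Prior and Concomitant Medications) gives two definitions. On the start date: "Medications which start prior to first dose will be considered prior medications". On the end date: "Ongoing medications and medications ending after the date of first dose will be considered concomitant medications". The classes can overlap, so a drug begun before dosing and continued afterwards is both. For unclear dates it adds: "Incomplete start and end dates which could be either prior to first dose or after first dose will be considered prior to first dose". The classification feeds a table: "Concomitant medications will summarize drug class and preferred name by treatment group and overall for each population". All prior and concomitant medications also appear in a by-subject listing.

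SAP 6.1.5 (Handling of Dropouts or Missing Data) has a different partial-date rule. A missing day becomes the first of the month "unless the month is the same month as the first dose then the day will be that of first dose". A missing month is handled in the same way, with January as the default. The section then names a use for the rule, "Missing AE start dates will be imputed using partial date imputation rules as previously described in this Section", and limits its reach: "Missing data for other parameters will not be imputed for analysis unless otherwise defined". The opening of 6.1.5 is blacked out.

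SAP 6.9.2 (Adverse Events) completes the picture for events: "Treatment-emergent AEs (TEAEs) are defined as AEs with an onset on or after the date of the first study drug administration".

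**The concern.** A concomitant-medication table should show what participants took from dosing onwards. Under 6.6 an unknown end date is read as evidence that the drug stopped before the study dose. The post-dose use that such a table exists to capture is what the rule can remove.

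The records at risk are drugs taken between discharge and the end-of-trial contact, which protocol 4.1 places 2-5 days after discharge and uses to collect adverse events and medications not known earlier. Some of these drugs will be remedies for adverse events. If the event and the drug are both reported with the day missing, 6.1.5 and 6.9.2 make the event treatment-emergent while 6.6 puts its treatment before dosing. A reader of the tables would see the event without its remedy. Because the table is repeated for each population, so is the omission.

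**Working it through.** The plan states no figure here, so the check applies the two date rules to the same records.

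**Inputs.** The definitions and the unclear-date rule come from SAP 6.6, the imputation rule from SAP 6.1.5 and the treatment-emergent definition from SAP 6.9.2. The dates are hypothetical: study dose on day 15 of a month, drug truly taken on days 17 to 18 of that month.

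**Rules as applied.**
- Prior: start before day 15.
- Concomitant: ongoing, or end later than day 15.
- 6.6: an incomplete date that could lie on either side of day 15 counts as before it.
- 6.1.5, if used for medications: an incomplete date in the dosing month, or with only the dosing year known, becomes day 15.

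**Patterns.** The partial start has two forms (day missing; day and month missing) and the end has four, giving 2 × 4 = 8. Both forms of partial start give the same result, so each row below counts twice.

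| End date as recorded | Under 6.6 | With 6.1.5 substituted |
|---|---|---|
| Complete (day 18) | prior and concomitant | concomitant only |
| Ongoing | prior and concomitant | concomitant only |
| Day missing | prior only | neither |
| Day and month missing | prior only | neither |

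**Result under 6.6.** The last two rows are lost from the table: 2 × 2 = 4 of 8. The other 4 stay in, because the end date or the ongoing flag makes them concomitant whatever the start date.

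**Result with 6.1.5 substituted.** Again 4 of 8 are lost. The end date becomes day 15, and 6.6 requires an end later than the dose date; day 15 is not later than day 15. The loss therefore comes from how an unclear end date is handled, and adopting 6.1.5 does not cure it.

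**Result under the fix below.** None of the eight patterns shows that the drug ended before day 15, so all are concomitant: 4 already kept + 4 recovered = 8 of 8.

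**The matching adverse event.** A start with the day missing in the dosing month becomes day 15 under 6.1.5. Day 15 is on the dose date, so the event is treatment-emergent under 6.9.2. A drug with that same partial start and an unclear end is prior only.

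**Boundary cases.** With dosing on the 30th and the drug dated only to the following month, no date is ambiguous and both rules class it as concomitant. With a complete post-dose start and a partial end, the end cannot precede dosing, so 6.6 should not apply; code that applied it mechanically would leave the drug in neither class.

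**The case against.** The strongest reply is that this is a deliberate convention with almost no consequence. Three parts of that reply stand.

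First, a reader might infer that 6.6 contradicts 6.1.5. The visible text does not support that. Section 6.1.5 names adverse event start dates and leaves other data to separate definitions; 6.6 can be read as that definition for medications. The two differ in direction, but what is missing is a statement of which governs. The blacked-out opening of 6.1.5 prevents saying more.

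Second, a reader might infer that every partially dated drug is misfiled. It is not. Drugs truly stopped before dosing are classed correctly, and ongoing drugs and those with a known post-dose end stay in the table.

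Third, a reader might infer that a post-discharge analgesic filed as prior would look like a breach of the 5-day medication bar (protocol 5.1, criterion 5; protocol 5.2, criterion 9) and lead to exclusion from the per-protocol population. Nothing visible makes that link. SAP 6.6 assigns a class and not a date within those 5 days. Protocol 6.5 collects medications from 30 days before Screening, so prior does not mean recent. SAP 6.3 takes deviations from a separate file supplied before database lock, and protocol 9.3 has major ones identified before lock.

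Exposure is also narrow. The 12-hour assessments are in-house, rescue times are recorded (protocol 6.5.1), rescue has its own summary (SAP 6.7), and the adverse event record notes remedial drug therapy (protocol 10.3.3). None of this makes the class right for a drug truly taken after dosing with two unclear dates.

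**Conclusion.** The point holds in a narrow form and is minor. As written, 6.6 gives the wrong class to a drug truly taken after dosing, not ongoing, with ambiguous start and end dates. The drug is then missing from the concomitant-medication table, while a similarly dated adverse event counts as treatment-emergent.

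The 4 of 8 is a count of recording patterns, not an expected proportion of records. The documents give no rate of incomplete dates. That few records are affected is a judgement from the in-house day and the short follow-up. The by-subject listing still carries the record. The primary SPID0-8 analysis is not shown to depend on the class. The conclusion assumes that the redacted part of 6.1.5 contains no overriding rule for medication end dates.

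**What to change.** Replace the unclear-date sentence in SAP 6.6 with three statements:

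1. A medication is concomitant unless its recorded dates show that it ended before first dose.
2. Any drug reported at the end-of-trial contact as taken since discharge is concomitant, however incomplete its dates.
3. Section 6.6, and not 6.1.5, governs medication dates.

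The SAP should also say whether an unclear start date still gives the prior label. If it does, the recovered drugs will be shown as both prior and concomitant, which leaves the table correct.

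The cost is a few SAP sentences and a small change to the derivation, with no new data. There are two side effects. Some drugs truly stopped before dosing, but with ambiguous end dates, will be counted as concomitant. A drug whose complete end date equals the dose date would also enter the table, which 6.6 now excludes; if that is not wanted, limit the first statement to incomplete end dates.

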6.7 Rescue Medications

Rescue medications will be coded to preferred name and ATC classification of ingredients using the WHO-DDE.

Rescue medications will be summarized by drug class and preferred name by treatment group and overall for each population.

A by-subject listing of all rescue medications will be presented.

6.8 Analysis of Efficacy

CCI

CCI

For the purposes of analysis, dates of the subject assessments for efficacy will be populated programmatically when the time indicates a date change, i.e., the collection time of the time point went past midnight.

